## **2. STUDY DESIGN**

This is a phase II non-randomized, open-label study in patients with moderate to severe cGvHD who have failed to respond to, or are intolerant of first line therapy. Patients will receive combination therapy with two oral agents (belumosudil, ruxolitinib) with documented individual efficacy as second line in cGVHD treatment. A maximum of 63 participants are expected to be enrolled in Canada.

[figure not shown]
Participants will begin on 10 mg BID of oral ruxolitinib alone for one cycle (i.e. Cycle 1). Each cycle is equal to 28 days. Starting at cycle 2, they will take belumosudil in addition to ruxolitinib, at a dose of 200 mg OD or 200 mg BID (if on a PPI). Patients will remain on dual therapy for 48 weeks (i.e. 12 cycles), until progression of cGVHD, or intolerance to either agent, whichever occurs sooner. A safety visit will be conducted at the end of treatment, 28 days following end of treatment, as well as a remote follow up visit conducted 24 weeks following end of treatment.

The end points will include overall response rates at 24 weeks on treatment and failure-free survival at 48 weeks on treatment (i.e., 28 and 52 weeks on combination therapy) which adopts composite endpoints including: (1) requirement of additional treatment or switch over, (2) progression or flare-up of GvHD with/without ruxolitinib tapering, and (3) death from relapse/non-relapse mortality.

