### **2.1 Estimated Study Duration**

The enrollment period of the study is expected to be approximately 12-18 months. The screening period may last up to 14 days. The treatment period for an individual patient is expected to be approximately 52 weeks from the date of starting therapy (i.e., Cycle 1 Day 1). Patients will be followed for evidence of progression of cGVHD, survival, and unexpected toxicity (if any) for 24 weeks after the end of treatment visit.

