**Figure 1. Participant treatment schema**

## 3. OBJECTIVES

Primary Objectives	Primary Endpoints
To evaluate efficacy, tolerability and safety of combination treatment of belumosudil with ruxolitinib as second line therapy for steroid-refractory cGvHD.	
 
Efficacy will be assessed using overall response rate (ORR) as per the NIH cGvHD Consensus Response Criteria at 24 weeks of combination treatment (C8D1) of belumosudil with ruxolitinib (i.e., 28 weeks after C1D1).
 
Tolerability and safety will be assessed by the incidence and severity of adverse events (AEs) throughout the treatment duration using CTCAE v5.0 grading.
 

Secondary Objectives	Secondary Endpoints
To evaluate the response achievement with combination treatment of belumosudil with ruxolitinib as second line treatment for cGvHD.	
 
ORR as per the NIH cGvHD Consensus Response Criteria after 48 weeks of combination treatment of belumosudil with ruxolitinib (i.e., 52 weeks after C1D1).
 
Failure-free survival (FFS) after 24 and 48 weeks of combination treatment of belumosudil with ruxolitinib (i.e., 28 and 52 weeks after C1D1). FFS is defined as the time from treatment initiation until the occurrence of treatment failure.
 
Durable response rate in patients who achieve complete or partial response with combination treatment of belumosudil with ruxolitinib as assessed at 52 weeks from
 

	
C1D1. Durable response is defined as sustained improvement in symptoms or absence of disease progression from the time of treatment initiation.
 
4. Overall GvHD symptom burden improvement, serially measured with a modified Lee Symptom Scale (see Appendix D).

Exploratory Objectives	Exploratory Endpoints
To evaluate improvement in musculoskeletal involvement of sclerotic GvHD using the P-ROM score measurement.	1. Changes in the P-ROM score after 12, 24, and 48 weeks of combination therapy in patients who have developed sclerotic GvHD in musculoskeletal involvement of GvHD

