## 5. STUDY TREATMENT

### 5.1 Study Drug Administration

The Investigational Medicinal Product (IMP), Belmosudil, will be provided by Sanofi as 200 mg tablets.

Ruxolitinib will be dispensed as either 5 or 10 mg tablets, and will be obtained through the site's local pharmacy, as it will be administered per SOC.

All patients will receive open-label IMP. Responsibility for treatment of patients rests with the QI. Prior to initiating ruxolitinib (Cycle 1 Day 1), a tuberculosis skin test or interferon-gamma release assay should be performed in accordance with the approved JAKAVI® (ruxolitinib) product monograph to screen for latent tuberculosis infection, with results interpreted cautiously in immunocompromised patients. Positive results should prompt appropriate evaluation and management per institutional guidelines before starting isoniazid therapy. If the patient had been already treated with isoniazid prophylaxis for 6 months due to prior history of tuberculosis skin test or interferon-gamma release assay, this test will be exempted.

Eligible participants in this study will be started on ruxolitinib monotherapy orally at the standard recommended dose of 10 mg BID for 4 weeks (28 days). After one full cycle of ruxolitinib treatment (i.e., C2D1), the participant will have an AE assessment and, unless Grade  $\geq 3$  AE is observed, will continue on the same dose of ruxolitinib **plus** oral belumosudil 200 mg QD (or BID if receiving concomitant PPI) starting on C2D1.

In the event that the participant is experiencing Grade  $\geq 3$  AE(s) at the intended C2D1 visit assessment, treatment with belumosudil should not begin. This visit will be considered an unscheduled visit and the C2

D1 visit should be rescheduled. The participant can continue on ruxolitinib alone and should be followed for resolution of the Grade  $\geq 3$  AE(s). If the Grade  $\geq 3$  AE(s) improves to Grade  $\leq 2$  or resolves completely within 4 weeks, the participant will still be eligible to receive belumosudil. In this case, they should come back in for a true C2D1 visit and can complete all the necessary assessments as well as belumosudil dosing. If the Grade  $\geq 3$  AE(s) does not recover within 4 weeks, the participant will complete the End of Treatment visit and discontinue study. If there are any questions or concerns about the patient status and treatment in these scenarios, this should be discussed with the sponsor.

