### **10.7 Adverse Event Reporting Period and Follow up of AEs, SAEs, and AESIs**

The AE reporting period begins at the time the patient receives their first dose of study treatment (i.e., C1D1). All AEs, SAEs and AESIs must be followed until resolution or 28 days following the last dose of study treatment, whichever comes first. The QI shall provide follow-up information when available in a new follow-up SAE form. Resolution status of such an event should be documented on the eCRF.

Patients withdrawn from the study due to an AE will be followed until the AE has resolved. In the case of an SAE, the patient will be followed until clinical recovery or until progression has been stabilized or judged to be chronic. After discontinuation from protocol treatment, all patients will be followed for any ongoing or late toxicities. Patients will be seen for a Safety Follow up visit,  $28 \pm 7$  days after discontinuing treatment. Safety Follow up procedures will be completed as indicated in the Study Calendar.

The AE reporting period will end once 28 days have passed since the patient's last dose of study drug. Therefore, SAEs occurring after the last dose of study treatment that have been deemed by the QI as at least possibly related to protocol treatment, must be reported if it occurs within 28 days after discontinuation of the investigational products. In addition, any known untoward event of any severity that occurs subsequent to the AE reporting period that the Investigator assesses as at least possibly related to the study therapy (i.e., the relationship cannot be ruled out) should also be reported as an AE. Ongoing and non-resolved toxicities are followed until resolution back to baseline or  $\leq$  Grade 1 after off treatment, or until considered stable by the QI.

---

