Safety and tolerability (primary endpoint) will be assessed throughout the treatment duration using CTCAE v5.0 grading. Adverse events will be summarized descriptively, including: - Incidence (number and percentage) of AEs, SAEs, and AESIs by grade, system organ class, preferred term, and relationship to study drug (belumosudil, ruxolitinib, or combination). - Frequencies and percentages for AEs leading to dose modifications, interruptions, or discontinuations. - Time-to-first AE (for key events) using Kaplan-Meier estimates if appropriate. No formal hypothesis testing will be performed for safety; results will be presented in tabular and graphical formats.

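### The adverse-event window opens at C1D1 but the safety population opens at the first belumosudil dose, so the primary safety incidence describes neither the combination nor the planned regimen

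*Protocol*

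**What the plan says.** The primary objective in Protocol section 3 is "To evaluate efficacy, tolerability and safety of combination treatment of belumosudil with ruxolitinib as second line therapy for steroid-refractory cGvHD". The matching endpoint there reads: "Tolerability and safety will be assessed by the incidence and severity of adverse events (AEs) throughout the treatment duration using CTCAE v5.0 grading". Section 11.3.1 repeats that window for the analysis: "Safety and tolerability (primary endpoint) will be assessed throughout the treatment duration using CTCAE v5.0 grading".

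Section 2.1 defines the period: "The treatment period for an individual patient is expected to be approximately 52 weeks from the date of starting therapy", counted from C1D1. Section 10.7 opens AE collection at the same point, the first dose of study treatment. Under sections 2 and 5.1 that dose is ruxolitinib alone for one 28-day cycle, with belumosudil added at C2D1. If a Grade 3 or higher AE is present at the intended C2D1, belumosudil is withheld and the visit rescheduled. The patient may start belumosudil if the event improves to Grade 2 or lower within 4 weeks, and otherwise leaves the study.

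Section 11.2 defines the safety population, the one evaluable for adverse events, as enrolled patients with at least one dose of belumosudil. Section 11.3.1 tabulates AEs by grade, system organ class, preferred term and relationship to belumosudil, ruxolitinib or the combination. It gives no split by onset before or after the first belumosudil dose.

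**The concern.** Three elements of the safety endpoint start at different points. The objective concerns the combination, the numerator starts at C1D1, and the denominator starts at the first belumosudil dose. A patient whose only Grade 3 or higher AE occurred on ruxolitinib alone and then settled is counted in the primary safety incidence. A patient with the same event that did not settle in time is not counted at all. Whether a lead-in event enters the table depends on its outcome and on later treatment.

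Elsewhere the protocol keeps the two clocks apart. Section 3 defines response after 24 weeks of combination treatment and equates this with 28 weeks after C1D1, and the P-ROM changes are timed from combination therapy. Safety has no combination clock.

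At stake is how the primary safety result can be read. This is a single-arm study, so the lead-in is its only view of ruxolitinib alone, and pooling hides it.

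**Working it through.** **1. Timeline.** 4 weeks of ruxolitinib alone (section 5.1) + 48 weeks of dual therapy (section 2) = 52 weeks, which reproduces the stated treatment period. The lead-in is 4/52 = 7.7% of treatment time for the standard patient. With the full extension it is 8/56 = 14.3%, but only for patients with a Grade 3 or higher AE at the intended C2D1.

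**2. Who is counted, following the text as written.**

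| Patient | In safety population (11.2)? | Lead-in AE counted (10.7, 11.3.1)? |
|---|---|---|
| Lead-in AE, belumosudil started on time | Yes | Yes |
| Grade ≥3 AE at intended C2D1, improves within 4 weeks, belumosudil started | Yes | Yes |
| Grade ≥3 AE at intended C2D1, not recovered within 4 weeks | No | No |
| Leaves in the lead-in for another reason | No | No |

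**3. Effect of the early window among belumosudil-treated patients.** The protocol states no AE rate, so these inputs are assumptions: 40% with a Grade ≥3 AE over the 52 weeks, and a lead-in hazard r times the later hazard, with r from 1 to 3.

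- Total cumulative hazard: H = −ln(1 − 0.40) = 0.511.
- Share arising on the combination: 48 / (48 + 4r).
- Combination-only incidence: 1 − exp(−H × share).
- r = 1: share 48/52 = 0.923, incidence 37.6%, difference 2.4 points.
- r = 3: share 48/60 = 0.800, incidence 33.5%, difference 6.5 points.

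As a sensitivity check, fix instead the incidence p over the combination window plus 28 days (48 + 4 = 52 weeks). The hazard is h = −ln(1 − p)/52, and a 4-week lead-in adds [1 − exp(−h(52 + 4r))] − p. At r = 1 this is 0.7, 1.9 and 2.6 points for p = 10%, 30% and 50%. For r from 0.5 to 3 over the same values of p, the range is 0.4 to 7.4 points.

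**4. Effect of the late denominator.** Assume all 63 patients receive ruxolitinib, k leave in the lead-in with an unrecovered Grade ≥3 AE, and about 30% of the rest have such an AE.

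| k | Reported (safety population) | All treated |
|---|---|---|
| 1 | 19/62 = 30.6% | 20/63 = 31.7% |
| 3 | 18/60 = 30.0% | 21/63 = 33.3% |
| 6 | 17/57 = 29.8% | 23/63 = 36.5% |

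Steps 3 and 4 compare the reported figure with two different targets. It lies above the combination-only incidence and below the whole-regimen incidence, by amounts that depend on rates the protocol does not give.

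**The case against.** The strongest reply is that phase-split tables, rules for worsening events and the origin of a time-to-event clock belong in the SAP, which is not at hand and may supply them. The list in section 11.3.1 is not exhaustive and excludes no such split. That reply stands for the table layout, and it means the problem may already be partly resolved. It does not cover the window and the population, which the protocol fixes itself and which do not match.

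Second, relationship to each drug is recorded (section 10.3) and tabulated. A Cycle 1 event precedes any belumosudil, so dates alone rule out attribution to it. This holds for the belumosudil-related rows. Ruxolitinib-related events can occur in both phases, however, and the all-cause rows remain mixed.

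Third, reporting the whole planned regimen from C1D1 is legitimate. That is true, but it would need everyone who started the regimen in the denominator, and section 11.2 leaves some of them out.

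Fourth, the consequence is limited. Safety carries no hypothesis test, and the stopping rules in section 5.9 turn on individual related events or the first three patients, not on pooled incidence. This stands. A before-and-after comparison of 4 weeks with 48 in one arm would also confound drug with time, so the lead-in would not isolate what belumosudil adds.

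**Conclusion.** The mismatch is real: followed as written, the protocol produces a primary safety incidence that measures neither the combination nor the planned regimen. For crude Grade 3 or higher incidence among belumosudil-treated patients, a 4-week lead-in adds about 2 to 6 points over a combination-only window. That rests on an assumed 40% incidence and a lead-in hazard 1 to 3 times the later one.

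Two stronger readings are not supported. A reader might infer that the result overstates the combination's toxicity outright. This holds only for crude incidence in belumosudil-treated patients against a combination-only window. Against the all-treated regimen the figure may be too low, so the net direction is not known.

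A reader might also apply an 8-week lead-in to the whole cohort. With a threefold hazard, the share is 48/(48 + 24) = 0.667 and the combination-only incidence 28.9%, a gap of about 11 points. But the extension is open only to patients who already have a Grade 3 or higher AE at the intended C2D1. Their lead-in incidence is 100% by definition, not the 15.7% that this calculation implies.

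The point affects how the safety result is read. It does not touch the efficacy decision or the stopping rules.

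**What to change.** Amend sections 11.2 and 11.3.1 so that each safety summary has a matching window and denominator:

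- **Combination:** in patients with at least one belumosudil dose, tabulate AEs with onset, or worsening in grade, on or after the first belumosudil dose. Base the combination safety conclusion on this table and start its time-to-first-AE clock at that dose.
- **Lead-in and whole regimen:** define a second population of all patients who received any study drug. Tabulate their AEs from C1D1, once for the lead-in and once for the whole regimen.

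The first part alone would still leave out patients who stop before belumosudil, so both are needed. If the SAP already contains these tables, the protocol definitions should be aligned with it.

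The cost is one derived flag, a second population definition and additional tables. AE start dates (section 10.2) and dosing data (section 11) are already collected, so no new data or visits are needed.

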Study Design:	This is a phase II, non-randomized, open-label study in patients with moderate to severe cGvHD who have failed to respond or are intolerant of first-line steroid therapy. Patients will receive combination therapy with two oral agents (belumosudil, ruxolitinib) with documented individual efficacy as second line treatment in cGvHD patients.

	Participants will begin on 10 mg BID of oral ruxolitinib monotherapy for one cycle (i.e. Cycle 1). Each cycle is equal to 28 days. Upon the initiation of Cycle 2, patients will begin taking belumosudil in addition to ruxolitinib, at a dose of 200 mg OD or 200 mg BID (if on a PPI). Patients will remain on combination therapy for 48 weeks (i.e. 12 cycles), until progression of cGVHD, or intolerance to either agent, whichever occurs sooner. A visit will be conducted at the end of treatment, 28 days post-end of treatment as well as 24 weeks (6 months) post-end of treatment.
Duration:	The enrollment period of the study is expected to take 12-18 months. The screening period for each patient may last up to 14 days. The treatment period for an individual patient is expected to be approximately 52 weeks from the date of starting therapy (Cycle 1 Day 1). Patients will be followed for evidence of progression of cGVHD, survival, and unexpected toxicity (if any) for 24 weeks after the end of treatment visit.
Planned Total Sample Size:	A maximum of 63 patients will be enrolled.
Investigational Product Administration:	Belumosudil will be administered as an oral dose of 200 mg OD or 200 mg BID (if patient is on a proton pump inhibitor (PPI))

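### Kaplan-Meier for time to first key AE has to censor deaths without the AE, so 1 minus Kaplan-Meier would modestly overstate cumulative incidence in a supportive display

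*Protocol*

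**What the plan says.** Section 3 makes tolerability and safety the second primary endpoint, "assessed by the incidence and severity of adverse events (AEs) throughout the treatment duration using CTCAE v5.0 grading". Section 11.3.1 puts this into practice with descriptive summaries. The first is "Incidence (number and percentage) of AEs, SAEs, and AESIs by grade", broken down further by system organ class, preferred term and relationship to study drug. Counts of AEs that led to dose changes or discontinuation follow. The last item is "Time-to-first AE (for key events) using Kaplan-Meier estimates if appropriate". The same paragraph rules out formal testing of safety. The synopsis lists only the frequency-type summaries for safety and does not mention Kaplan-Meier there.

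On observation time, Section 10.7 states that "The AE reporting period will end once 28 days have passed since the patient's last dose of study drug". It then adds that "any known untoward event of any severity that occurs subsequent to the AE reporting period" is still to be reported if the investigator judges it at least possibly related. Combination treatment runs for 48 weeks, "until progression of cGVHD, or intolerance to either agent, whichever occurs sooner" (synopsis). Section 10.9 keeps deaths from progressive disease and relapses of the malignancy out of SAE reporting.

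**The concern.** Death without the key AE rules out that AE for good. In a Kaplan-Meier estimate of time to first AE such a death can only be censored. If it were counted as an event, the curve would show AE-free survival, which is a different quantity. The estimate then describes AE risk in a population in which nobody dies, and 1 minus the curve exceeds the proportion of treated patients who experience the event. Section 10.9 makes this concrete: deaths from progression would not normally enter an AE curve as events.

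The other time-to-event endpoints in Section 11.3.1 are not exposed in this way. Durable response counts death from any cause as an event, and failure-free survival counts relapse and non-relapse mortality as failures. The AE line has no such provision. At stake is a curve for a key AE, such as Grade 3 or higher infection, that runs somewhat high and does not match the percentages reported beside it.

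**Working it through.** The protocol gives no AE rate, death rate or cumulative-incidence figure, so there is nothing of its own to reproduce. The size has to be shown over assumed rates.

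**Inputs**
- Horizon: 52 weeks of treatment (Section 2.1).
- Patients: 63 enrolled (Section 11.1). The safety population requires a dose of belumosudil and may be smaller.
- Net risk of the key AE by week 52, *a*: 20, 30 or 40% (assumed).
- Probability of a competing event by week 52 in the absence of the AE, *c*: 5 or 10% (assumed). The 10% dropout allowance in Section 11.1 is the only related figure, and it is an allowance for the response endpoint, not a death rate.

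**Formulas**, with constant cause-specific hazards over the 52 weeks
- λa = −ln(1 − a) and λc = −ln(1 − c).
- 1 minus Kaplan-Meier, competing events censored: 1 − exp(−λa) = a.
- Cumulative incidence: λa/(λa + λc) × [1 − exp(−(λa + λc))].

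**Example**, a = 30%, c = 10%: λa = 0.3567 and λc = 0.1054. The cumulative incidence is 0.3567/0.4620 × (1 − 0.70 × 0.90) = 0.772 × 0.37 = 28.6%. The excess is 30.0 − 28.6 = 1.4 points.

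| 1 − KM | c | Cumulative incidence | Excess (points) |
|---|---|---|---|
| 20% | 5% | 19.5% | 0.5 |
| 20% | 10% | 19.0% | 1.0 |
| 30% | 5% | 29.3% | 0.7 |
| 30% | 10% | 28.6% | 1.4 |
| 40% | 5% | 39.1% | 0.9 |
| 40% | 10% | 38.1% | 1.9 |

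In relative terms the excess is about 2 to 5%. Against sampling error it is small. In the example the binomial SE is √(0.286 × 0.714/63) = 5.7 points, so 1.4 points is about 0.25 SE. In the last row, √(0.381 × 0.619/63) = 6.1 points, so 1.9 points is about 0.3 SE.

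**Finite-sample check.** In 4,000 simulated trials of 63 patients with net AE risk 30%, death 10% and treatment stop 20%, 1 minus Kaplan-Meier averaged 30.0%. Aalen-Johansen with death alone as competing averaged 28.5%. With treatment stop also treated as competing it averaged 25.8%. Over the four settings simulated, the excess from death alone was 0.5 to 1.8 points. The further 2.7 points in this setting (28.5 − 25.8) come from changing the question to strictly on-treatment AEs. They are not part of the error claimed here.

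**The case against.** The strongest reply is that the protocol states no censoring rule, does not define the key events, and does not say that 1 minus Kaplan-Meier will be presented as cumulative incidence. The display is conditional on being appropriate, and such detail usually belongs in the SAP. Most of that is true and limits the point. It does not remove it, because the protocol itself fixes the estimator, and that estimator has no place for death except as censoring.

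A second reply is that Aalen-Johansen adds little. With complete follow-up, and with both death and end of AE observation as competing events, its value at the end of follow-up equals the crude proportion that Section 11.3.1 already reports. That is correct for that version. What remains is a curve over time that agrees with the table.

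A reader might go further and infer three things that the protocol does not support:
- *That a primary endpoint is misstated.* The main summary of the safety endpoint is the crude number and percentage, which this choice of estimator does not touch.
- *That stopping treatment makes an AE impossible, so every stop is a competing event.* Section 10.7 collects AEs for 28 days after the last dose and related ones after that. Whether the end of observation is a competing event or censoring depends on the quantity wanted.
- *That the excess is large because non-responders leave early.* Section 5.6 allows patients with lack of response or mixed response to continue with sponsor approval, so non-response rates cannot stand in for exit rates.

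**Conclusion.** The point stands as a minor improvement to a stated method. Kaplan-Meier is a poor choice for time to first key AE because deaths without the AE are censored, and 1 minus the curve then overstates cumulative incidence. The direction is certain wherever such deaths occur. The size is about 0.5 to 2 points at 52 weeks, roughly 0.1 to 0.3 SE, if 5 to 10% of patients have a competing event and the net AE risk is 20 to 40%. Those rates and the constant hazards are assumptions. Only a supportive, descriptive and untested display is affected; neither the crude AE percentages nor the response-based success rule in Section 11.1 changes.

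**What to change.** In Section 11.3.1, replace the time-to-first-AE item with: *cumulative incidence of first key AE by the Aalen-Johansen estimator with 95% CI, with death without the event as a competing event.*

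Add one clause on the quantity wanted. If the display is meant to be strictly on-treatment, the end of AE observation (28 days after the last dose) may also be treated as a competing event, and the display should be labelled so. Otherwise the end of observation is censoring.

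The cost is a sentence or two and standard software. No new data, visits or patients are needed.
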